4.6 DATA MANAGEMENT

A Data Management Plan will be created before the start of data collection and will describe all functions, processes, and specifications for data collection, cleaning and validation to ensure that the data are as clean and accurate as possible when presented for analysis. Data collection and validation procedures will be detailed in the appropriate operational documents.

A study monitoring plan, including for-cause monitoring, that is appropriate for the study design will be developed and implemented. Data quality control (QC) will be performed remotely and at the center level, where permissible according to local regulations, by qualified designated personnel under professional secrecy.

All medical data will be confidential. Pierre Fabre Médicament, as the Sponsor of the study and data controller, is responsible for the processing of personal data in accordance with the provisions of Regulation 2016/679/EU of the European Parliament and of the Council of 27 April 2016 on the protection of natural persons with regard to the processing of personal data and the free movement of such data (GDPR), the data collected being for research purposes in the field of health, the legal basis of the processing being the legitimate interest of the data controller.

Data from patient medical records will be entered by the investigator or delegated data entry specialists in the eCRF. The qualified designee for data entry must ensure that:

- Data entry is performed in a timely manner,
- Data entry is complete and accurate,
- All eCRF data are verifiable in the source documentation,
- Data queries are resolved and documented by authorized study staff,
- All eCRFs are approved with an electronic signature (changes to data previously submitted will require a new electronic signature to acknowledge/approve the changes).

All data collected within the eCRF will be approved and electronically signed and dated by the investigator. This approval will acknowledge the investigator's review and acceptance of the data as being complete and accurate.

At study end and before the final statistical analysis, the eCRF and other study data will be locked to further additions or corrections. Locking the study data represents the acknowledgement that all data have been captured and confirmed as accurate.

Quality assurance department representatives from Pierre Fabre Médicament and/or Contract Research Organization (CRO) may visit a study center to conduct quality assurance audit and ensure the study is conducted in compliance with protocol, Standard Operating Procedures and all applicable legal requirements.

4.7 DATA ANALYSIS

4.7.1 General considerations

Statistical analyses will be fully described in a Statistical Analysis Plan (SAP). Analyses will be conducted with SAS® software, version 9.4 or higher.

Analyses will be descriptive in nature, as no hypothesis will be tested.

Demographic and clinical characteristics will be presented in the overall population using usual statistics. Quantitative data will be summarized as median, min, max and number of missing data. Qualitative variables will be described as number, percentage and number of missing data.

4.7.2 Data-set definition

Analysis population (full analysis set) consists of all patients fulfilling inclusion and exclusion criteria with at least one QoL score not missing.

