4.5 STUDY SIZE

Within this study, it is planned to recruit 156 patients.

Accrual of 140 evaluable patients permits to estimate a 95% confidence interval of a proportion equals to 40% with an accuracy of +/-8%. The following table presents the accuracy for different proportions:

	Proportion of DLQI score ≥ 6			
	10%	20%	30%	40%
Accuracy (%)	+/-5	+/-6.5	+/-7.5	+/-8

Assuming a rate of around 10% of non-evaluable patients (missing data), 156 patients will be included to reach 140 evaluable patients.

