4.7.3 Analysis of primary outcomes

The primary endpoint is the rate of patients with a DLQI score ≥ 6 . It will be described as number and percentage with corresponding 95% interval (binomial exact).

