4.7.6 Missing data

In general, missing data will not be imputed (except for dates) and the data will be analyzed according to the complete case approach. Proportion of missing data will be provided for all variables during descriptive analyses.

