comprehensively filled. Sensitivity analyses may be carried out, where applicable, to estimate the impact of missing data on the study's outcomes. Furthermore, if a non-negligible proportion of missing data is observed for a certain parameter, groups of patients with and without missing data may be compared.

PROs will be collected with tablets, which minimizes the number of missing data through the use of drop-down lists and mandatory fields.

4. Memory bias:

As dermatological events will be collected during the last 2 years (up to 1 year and 9 months) to 3 years (up to 3 years and 6 months), they could be underestimated reported number of punctual or mild dermatological toxicities.

5. Heterogeneity between study centers:

Since this is an observational study of real-life dermatological toxicities, reporting of toxicities can vary widely based on standard practices in each country and/or investigating center. This could lead to an over or under-reporting of certain data. Where deemed appropriate subgroup analyses by country could be performed for certain outcomes or variables of interest.

6. Measurements bias:

Data regarding primary and secondary outcomes are mainly declarative data collected directly from patient and may thus not completely reflect reality. Data collected through self-questionnaire which are completed by the patient may lead to a reporting bias. However, as this is data related to quality of life and facts experienced by patients, this collection method was the best compromise. To maintain confidentiality and to avoid bias, data gathered at the patient level will not be accessible to investigators and only be processed in the research perspective of this study.

Further details on how biases in the study design are to be addressed will be elaborated in the SAP.

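### The only analysis set requires a questionnaire score, so eligible women without one drop out of toxicity outcomes that need no questionnaire

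*Protocol*

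**What the plan says.** Section 4.7.2 gives the only set definition in the protocol: all patients who meet the eligibility criteria, "with at least one QoL score not missing".

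The outcomes analysed in it have different sources:

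- **Primary (4.3.1, 4.7.3):** "The primary endpoint is the rate of patients with a DLQI score" of 6 or more, with an exact binomial 95% interval. It comes from the patient questionnaire.
- **Ongoing toxicities (4.3.2 item 2, 4.7.4):** reported by the investigator under CTCAE version 5.0. Frequency and percentage with a 95% CI are promised for each event.
- **Toxicity history (4.3.3, 4.7.5) and clinical characteristics (4.3.2 item 3):** taken from medical charts according to section 4.1. Section 4.7.1 presents the characteristics in an overall population, a term that is not defined.

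On missing data, section 4.7.6 states that, in general, "the data will be analyzed according to the complete case approach", with imputation only for dates. Section 4.5 budgets for the loss: "Assuming a rate of around 10% of non-evaluable patients (missing data), 156 patients will be included to reach 140 evaluable patients". It does not say what makes a patient evaluable. Section 4.10 (item 3) accepts that data not missing completely at random can bias the descriptions, and then says "Sensitivity analyses may be carried out, where applicable, to estimate the impact of missing data". Sections 4.7.1, 4.7.4 and 4.7.6 commit to reporting how much is missing, and 4.7.4 also commits to profiles of missing scores.

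**The concern.** Entry to the set depends on a patient-reported score, but the toxicity outcomes do not. A woman who meets the criteria, consents, and then does not start or finish the questionnaires can still have a full investigator assessment and a full chart history. Under 4.7.2 she is in no defined set, so her toxicities are not counted.

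Describing toxicities in this population is a stated aim of the study, and section 4.10 is already concerned with representativeness. Restricting prevalence to questionnaire completers adds a selection step that serves no purpose. If women who do not complete differ in toxicity burden from those who do, each reported percentage is shifted, and its confidence interval does not reflect this.

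The primary rate raises a related but smaller matter. The plan expects some women to be non-evaluable and names the bias this could cause, but it fixes nothing in the protocol to show how far the rate could move.

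**Working it through.** **1. The plan's own figures reproduce.**

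- Inclusion number: 140 / (1 − 0.10) = 155.6, rounded up to 156, as stated in 4.5. That leaves 156 − 140 = 16 non-evaluable women.
- Precision at 40%: 1.96 × √(0.40 × 0.60 / 140) = 8.1 points, against the stated 8.

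No stated figure is wrong.

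**2. Who falls out of the toxicity outcomes.** Set against the definition in 4.7.2, there are three kinds of eligible woman:

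| Questionnaires available | In the 4.7.2 set? | Counted in DLQI rate (complete case)? | Counted in toxicity outcomes? |
|---|---|---|---|
| DLQI present | yes | yes | yes |
| DLQI missing, another score present | yes | no | yes |
| no score at all | no | no | no, although the data exist |

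Only the last row is a problem. The protocol does not say how many women it contains. Section 4.5 speaks of non-evaluable patients in general, so the number k of women with no score could be anything from 0 to 16 under the plan's own assumption.

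**3. Size for a toxicity percentage.** Let p be the prevalence among women with a score and q the prevalence among the k women without one. The percentage over all 156 differs from p by (k / 156) × (q − p). Assume p = 30% (an illustration, since the protocol gives no value) and let q range from half to twice p, that is 15% to 60%:

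- k = 4: from 4/156 × (−0.15) = −0.4 points to 4/156 × 0.30 = +0.8 points.
- k = 16: from 16/156 × (−0.15) = −1.5 points to 16/156 × 0.30 = +3.1 points.

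The gain in precision is minor even at the maximum. The half-width is 1.96 × √(0.21/140) = 7.6 points with 140 women and 1.96 × √(0.21/156) = 7.2 points with 156.

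**4. Size for the primary rate.** Assume all 16 non-evaluable women lack a DLQI and the observed rate is 56/140 = 40.0% (exact 95% interval 31.8% to 48.6%):

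- All 16 below the cut-off: 56/156 = 35.9%.
- All 16 at or above it: (56 + 16)/156 = 72/156 = 46.2%.
- The distance between the extremes is 16/156 = 10.3 points, whatever the observed rate.
- Milder case, with the rate among missing women between half and twice the observed 40%: (56 + 16 × 0.20)/156 = 37.9% to (56 + 16 × 0.80)/156 = 44.1%. The shift is about 2 to 4 points.

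**The case against.** The strongest case on the other side is that few women should have no score at all. Questionnaires are filled in on site on study tablets (4.4) with mandatory fields (4.10), after consent (4.2.2.2), and women unable to complete them are excluded (4.2.1.2, criterion 1). This stands, and it is why the effect is likely small. It does not remove the problem, since mandatory fields prevent skipped items but not a set that is never started or is abandoned.

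Four stronger readings are tempting, and the documents do not support them.

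- **That missing data would go unreported.** Sections 4.7.1, 4.7.4 and 4.7.6 commit to giving numbers or proportions missing, and 4.7.4 to missing-score profiles. Section 4.10 also foresees, as an option, comparing patients with and without missing data.
- **That the set is too wide for the primary endpoint.** A woman with only a Hairdex score is in the set, but under the complete-case rule she does not enter the DLQI rate. No primary result changes.
- **That characteristics are certainly restricted to completers.** The reference to an overall population in 4.7.1 may mean all included women. The fault there is ambiguity.
- **That lacking a fixed sensitivity method is an error.** Sections 4.7.1 and 4.10 defer such detail to the SAP, which is not at hand. A protocol commonly leaves this to the SAP.

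The same 16 women also cannot be assigned freely. Those who lack only the DLQI stay in the set and lose no toxicity data. The 7.6 to 7.2 point comparison requires all 16 to lack every questionnaire, which 4.5 does not say.

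**Conclusion.** The point holds for the analysis set. Section 4.7.2 fixes one population that depends on a questionnaire score and gives no reason for applying it to investigator- and chart-based toxicity outcomes. The population for characteristics is left unclear. This is a minor defect that is easily corrected. Its effect is zero if every woman has at least one score. In the illustration above it reaches about 3 points for a 30% toxicity, and only if all 16 women lack every score and have twice the prevalence.

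For the primary rate, the complete-case denominator is workable and the stated precision is right. The range of 35.9% to 46.2% assumes that all 16 women lack a DLQI and all fall on one side of the cut-off. It marks the limits of what missing data could do, not the bias to expect, and both values lie inside the exact complete-case interval. It supports adding a line to the report, not a claim that the planned estimate is invalid.

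**What to change.** - **4.7.2:** define a set of all eligible consenting women and use it for ongoing toxicities, toxicity history and demographic and clinical characteristics. Keep women with a DLQI score as the denominator of the primary rate, and say so.
- **4.7.1:** state that the overall population is this set of all eligible consenting women.
- **4.5:** say what evaluable means, most simply having a DLQI score.
- **4.7.3, or the SAP:** add one line giving the primary rate over all eligible women with every missing DLQI counted first as below 6 and then as 6 or more, next to the complete-case rate and the number missing.

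No new data are needed and the sample size does not change. The cost is a few sentences and one table line. If few scores are missing, the bounds nearly coincide with the main result and show that it is robust.

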4.7.3 Analysis of primary outcomes

The primary endpoint is the rate of patients with a DLQI score ≥ 6 . It will be described as number and percentage with corresponding 95% interval (binomial exact).

4.7.4 Analysis of secondary outcomes

Quality of Life Scores will be calculated using recommendations provided in the literature and will be described by means, standard deviations, medians, and percentages. The percentage of missing Quality of life scores will be also provided and patients' missing score profiles will be then generated to assess the impact on QoL scores.

Dermatological toxicities ongoing at inclusion will be described. Each of the following will be assessed:

- Dermatological toxicities by type,
- Dermatological toxicities for each type and by grade.

Frequency, percentage with 95% Confidence Interval (CI) will be computed for each event.

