2.2 RATIONALE

The rationale for conducting this transversal real world observational study is the following:

- There is a lack of data regarding dermatological events impact on quality of life in early breast cancer females receiving adjuvant endocrine therapy: dermatological toxicities induced by adjuvant endocrine therapy can have a marked effect on cancer patients' quality of life but are rarely described in literature). This transversal real word observational study aims to describe the dermatological toxicities reported by patients with breast cancer treated with adjuvant endocrine therapy.
- The justification for the targeted population is the following:
 - Age and sex

Females aged above 18 years old will be considered in this study. Breast cancer mainly concern females as only 1% of males are affected according to ESMO (**Cardoso, 2019**). Considering females about a quarter of breast cancers occurred before age 50, and less than 5% before age 35 (**Cardoso, 2019**). The same range of proportion is therefore expected in the study to be representative of the general population.

- Early breast cancer status

All early breast cancer stages status according to WHO (**Tan, 2020, Cardoso, 2019; Lakhani, 2012**) and TNM classification (**Teichgraeber, 2021**) will be included in the study in order to have an overall view of the whole population of patients treated with adjuvant endocrine therapy for breast cancer. The cancer status will be reported in the characteristics baseline.

- Justification of the study timepoint

To avoid catching dermatological reactions related to prior treatments, only early breast cancer female patients treated, with ongoing adjuvant endocrine therapy in monotherapy initiated 2 years (up to 1 year and 9 months) to 3 years (up to 3 years and 6 months) ago will be included.

- Justification of the Quality of Life (QoL) questionnaires

For the primary objective, the Dermatology Life Quality Index (DLQI) questionnaire will be used for evaluating the overall quality of life regarding dermatological concerns.

For the secondary objectives, the QoL questionnaires were selected according to the common adverse events related to dermatological toxicities:

- Skindex-16 questionnaire for dermatological disease on quality of life (**Chren, 2012**),
- Hairdex questionnaire for evaluating of disease-specific quality of life in patients with hair diseases (**Fischer, 2001**),

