3.2 SECONDARY OBJECTIVES

Secondary objectives aim, in female patients with EBC, being treated with ongoing adjuvant endocrine monotherapy initiated 2 years (up to 1 year and 9 months) to 3 years (up to 3 years and 6 months) before inclusion in the study, to describe:

1. The dermatological quality, using Skindex-16, Hairdex, and ItchyQoL
2. The real-world dermatological toxicities present at inclusion.
3. The demographics characteristics, and the clinical characteristics.

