4.2.1.1 Inclusion criteria

Patients will be eligible for inclusion if they fulfill ALL The following criteria:

1. Female aged \geq 18 years at inclusion.
2. Histologically confirmed diagnosis of EBC, according to the WHO criteria (**Lakhani, 2012; Cardoso, 2019; Tan, 2020**) and the TNM classification, (**Teichgraeber, 2021**) at any time before inclusion.
3. Still being treated with adjuvant endocrine monotherapy, initiated 2 years (up to 1 year and 9 months) to 3 years (up to 3 years and 6 months) before the inclusion in the study.
4. Signed Informed Consent Form (ICF) or non-opposition, according to local regulations.

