4.2.1.2 Exclusion criteria

Patients will not be eligible for inclusion if they fulfill ANY of the following criteria:

1. Patients not able to read, understand and complete Questionnaires in local language.
2. Patients with chronic dermatological conditions (treated or not) before initiating the adjuvant endocrine therapy that could interfere with the quality of life.
3. Patients with concomitant targeted therapies with adjuvant endocrine therapy such as CDK4/6 inhibitors or trastuzumab, and patients with ongoing treatment with neratinib..
4. Patients having relevant or severe comorbidities requiring complex therapeutic treatment.
5. Patient having a persistent post-chemotherapy alopecia (at least of grade 1).

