4.3.2 Secondary outcomes

1. Quality of life data collected at the time of inclusion using the Skindex-16, Hairdex, and ItchyQoL questionnaires.

The Skindex-16 includes items distributed across three domains symptoms (items 1 to 4), emotions (items 5 to 11) and functioning (items 12 to 16) and are answered on a seven-point Likert scale (varying from 0-never bothered, to 6-always bothered), which represents the frequency with which the skin problem bothered the respondent during the past week. This is a 0-100 scale, higher the score, the more quality of life is impaired.

The Hairdex is a valuable tool for evaluating disease-specific QoL in patients with hair disorders. It consists of 48 questions across five sections: symptoms, functioning, emotions, self-confidence, and stigmatization. Each question is self-graded on a scale of 0-4, with a score of 4 indicating the most severe change from a patient's baseline quality of life.

The ItchyQoL is a questionnaire used to measure the QoL in patients with chronic pruritus. It is composed of 22 items regarding symptoms, functions, emotions and self-perception, and is currently under copyright protection. In addition to the total score, a subscore for "symptoms", "functioning" and "emotions" can also be calculated. Each item is rated on a 5-point scale, ranging from 1 = never to 5 = all the time.

2. Ongoing dermatological toxicities reported by investigator according to Common Terminology Criteria for Adverse Events (CTCAE) (version 5.0, November 2017):
 - a. Type of toxicity
 - b. Surface area involved (except for nails and oral dryness)
 - c. Start date
 - d. Clinical grading of the toxicity
3. Demographics, and clinical characteristics at the time of inclusion, including the following items:
 - a. Age, gender, weight, height
 - b. Menopausal status
 - c. Date of cancer diagnosis
 - d. Primary tumor location
 - e. T stage
 - f. Prior therapies for breast cancer (type, agent name, start date, stop date)

- g. Endocrine therapy (agent name, start date) for breast cancer
- h. Current dermatological care and sun-protective behaviors

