4.3.3 Exploratory outcomes

History of dermatological toxicities from the beginning of current treatment to the time of inclusion, including:

- a. Type of dermatological toxicity
- b. Surface area (except for nails and oral dryness)
- c. Start date and end date
- d. Grade of the toxicity, if available
- e. Change in hormonal treatment (adaptation, interruption), if applicable

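### Section 4.7.4 tabulates ongoing toxicities without using their start date, so the percentages can include persisting effects of treatment given before endocrine therapy

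*Protocol*

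**What the plan says.** **Objective and outcome.** Secondary objective 2 (Protocol 3.2) is "The real-world dermatological toxicities present at inclusion". The matching outcome in 4.3.2 is "Ongoing dermatological toxicities reported by investigator according to Common Terminology Criteria for Adverse Events (CTCAE"), recorded with type, surface area, start date and grade. It has no item on cause and no limit on onset.

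**Analysis.** Section 4.7.4 states "Dermatological toxicities ongoing at inclusion will be described", by type and by type and grade, with a frequency, a percentage and a 95% confidence interval for each event. The start date plays no part.

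**Contrast.** The exploratory outcome in 4.3.3 does carry an onset limit: "History of dermatological toxicities from the beginning of current treatment to the time of inclusion".

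**Window.** Inclusion criterion 3 (4.2.1.1) requires endocrine monotherapy "initiated 2 years (up to 1 year and 9 months) to 3 years (up to 3 years and 6 months) before the inclusion". Section 2.2 gives the reason: "To avoid catching dermatological reactions related to prior treatments".

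**Other safeguards** (numbered as in 4.2.1.2). Exclusion 2 removes women whose chronic skin disease predates endocrine therapy, if it might affect quality of life. Exclusion 3 removes concomitant targeted therapy and ongoing neratinib. Exclusion 5 is "Patient having a persistent post-chemotherapy alopecia (at least of grade 1").

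**Prior treatment.** Section 4.3.2 also collects "Prior therapies for breast cancer (type, agent name, start date, stop date"). Section 4.3.4 permits, but does not require, subgroups by prior radiotherapy, chemotherapy (with taxane use) and targeted therapy.

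**The concern.** The window is meant to keep reactions to earlier treatment out of the data. It guarantees a minimum time on endocrine therapy. It sets no interval since the end of other treatment and no condition on when a toxicity began. Exclusion 5 shows that the protocol itself expects at least one prior-treatment effect to outlast the window.

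The study is motivated by toxicities of endocrine therapy, and readers will take the table of ongoing toxicities in that light. If some of the counted events began before endocrine therapy, the table does not show how many. The information needed to show it is collected but not used.

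**Working it through.** **1. What the window controls.** The lower limit is 24 − 3 = 21 months and the upper limit is 36 + 6 = 42 months, both counted from the start of endocrine monotherapy. An event that began k months before that start and never resolved is 21 + k to 42 + k months old at inclusion. It is ongoing, so 4.7.4 counts it. No value of k is ruled out by the window.

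**2. What the exclusions leave.**
- Exclusion 5 covers alopecia after chemotherapy only.
- Exclusion 2 covers pre-existing chronic conditions only where they might affect quality of life. A low-grade nail or radiation-field change not judged to do so stays eligible. If exclusion 2 were meant to cover all sequelae of earlier treatment, exclusion 5 would be largely redundant.
- Exclusion 3 concerns concomitant treatment. Women with earlier targeted therapy remain and form one of the possible subgroups in 4.3.4.

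**3. Whether collection is limited to the endocrine period.** The protocol points both ways.
- For a limit: the Synopsis (Study design) and 4.1 describe chart collection of toxicities from the start of endocrine therapy, although the sentence in 4.1 is garbled. The memory-bias paragraph of 4.10 speaks of events over the last two to three years.
- Against a limit: 4.2.2.2 lists the history, with its limit, and ongoing toxicities, without one, as separate items. Sections 4.3.2 and 4.7.4 also give no limit for ongoing events.

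**4. Scale (illustration only).** The protocol gives no carry-over rate and no expected prevalence of any toxicity. Its precision table in 4.5 is for the DLQI proportion, but it serves as a yardstick at the same target of 140 evaluable patients. The half-width is 1.96 × √(p(1 − p)/140):
- p = 10%: 4.97 points (stated 5)
- p = 20%: 6.63 points (stated 6.5)

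For one toxicity type, let p be the prevalence with onset on endocrine therapy and q the prevalence carried over from earlier treatment. Both are assumed, and they are taken as independent. Then reported prevalence = 1 − (1 − p)(1 − q), and excess = (1 − p)q.

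| q | reported, p = 10% | excess (points) | reported, p = 20% | excess (points) |
|---|---|---|---|---|
| 0% | 10.0% | 0 | 20.0% | 0 |
| 2% | 11.8% | 1.8 | 21.6% | 1.6 |
| 5% | 14.5% | 4.5 | 24.0% | 4.0 |
| 10% | 19.0% | 9.0 | 28.0% | 8.0 |
| 20% | 28.0% | 18.0 | 36.0% | 16.0 |

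The excess passes the half-width at q = 4.97/0.90 = 5.5% for p = 10%, and at q = 6.63/0.80 = 8.3% for p = 20%.

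**The case against.** **The objective is descriptive.** It concerns toxicities present at inclusion, and 4.3 calls the outcomes purely descriptive. A reader might infer that prior-treatment effects will be reported as endocrine-therapy toxicities. The documents do not support that: 4.7.4 attributes no cause, and causal wording appears only in the rationale. What stands against the objection is that the window is justified by keeping other causes out, and the table as stated cannot show whether it did.

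**The window is not the only safeguard.** This is correct. Exclusions 2, 3 and 5 all act against carry-over, and many long-lasting pre-existing skin conditions would be caught by exclusion 2. It would be wrong to say that the purpose fails for every type except alopecia.

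**The clock starts with monotherapy.** Other systemic therapy may fairly be taken to have ended by then. The footnote to Figure 1 in 2.1, which shows radiotherapy and anti-HER2 therapy alongside endocrine therapy, annotates a guideline algorithm and not this study's eligibility. This narrows the concern. It does not remove events that began earlier and persist, and radiotherapy overlapping the start of endocrine therapy could remain.

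**The passages on chart collection imply an onset limit.** They do so in part, and that limit may be the intention. The outcome definition and the analysis section do not repeat it.

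**The SAP may settle it.** It may, and it is not shown. But the protocol states the tabulation and sets an onset limit for the exploratory outcome, so it is reasonable to improve the stated tabulation here.

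**Conclusion.** The point holds as a possibility that the stated tabulation leaves open. The percentages in 4.7.4 can include persisting effects of earlier treatment that exclusions 2, 3 and 5 do not remove. How large that share is cannot be derived from the documents, and it may be zero. The illustration shows only that a carry-over of roughly 5 to 8% in one type would already match the sampling error at 140 patients. It rests on assumed prevalences and on independence.

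A reader might also infer an inflated overall figure, for example 40% of women with any toxicity rising to 46–52% under an assumed 10–20% carry-over (1 − 0.6 × 0.9 and 1 − 0.6 × 0.8). The documents do not support that figure. Section 4.7.4 plans no any-toxicity composite, and the protocol's only 40% is a DLQI proportion.

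The change is worth making because it is cheap, serves the aim stated in 2.2 and uses data already collected.

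**What to change.** - **Section 4.7.4:** report each ongoing toxicity type and grade in three rows by recorded start date: on or after the endocrine therapy start date, before it, or undatable. Base the split on recorded dates. Section 4.7.6 allows dates to be imputed, and an imputed onset could fall on the wrong side of the treatment start.
- **Section 4.7.4:** describe the time from the last prior therapy to inclusion, using the stop dates already collected. The onset split cannot separate effects of radiotherapy that overlapped the start of endocrine therapy, and this description gives the reader the context.
- **Section 2.2:** say that the window reduces carry-over from prior treatments and does not avoid it. The Synopsis rationale uses the same wording and should match.

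The cost is protocol or SAP wording and one or two derived variables. Nothing new is collected and eligibility does not change. The downside is that some events with partial or missing dates will fall in the undatable row.
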